7.6 Survival Follow-up (\pm 2 weeks)

The survival follow-up period refers to the time between disease progression (or confirmed disease progression in cases where Investigator treats beyond initial progression as outlined in section [8.2](#)) and patient death. Survival status and subsequent anti-cancer therapy will be collected approximately every 12 weeks in a clinic visit, or by telephone. Patients who withdraw consent for study procedures should still be followed for survival and/or public records searched as per FDA guidance issued October 2008 entitled "Guidance for Sponsors, Clinical Investigators, and IRBs: Data Retention When Subjects Withdraw from FDA-Regulated Clinical Trials".

8.0 STUDY ASSESSMENTS

8.1 Safety Assessments

8.1.1 Safety Analysis

Safety data will be tabulated for all patients and include vital signs, laboratory parameters, and adverse events.

8.1.2 Reporting of Adverse Events

8.1.2.1 Adverse Events

An adverse event (AE) is any untoward medical occurrence in a patient or clinical investigation subject administered a pharmaceutical product that does not necessarily have a causal relationship with the treatment. An adverse event can be any unfavorable and unintended sign (including a laboratory finding), symptom or disease temporally associated with the use of a medicinal (investigational) product, whether or not related to the medicinal (investigational) product.

The AE reporting period starts on Cycle 1 Day 1; if an AE occurs before the first dose of study treatment it will be captured as baseline and considered a part of the medical history; however, if the AE is directly attributed to a study procedure prior to C1D1, it may be reported as an AE. At each evaluation, patients should be interviewed in a non-directed manner to elicit potential adverse reactions from the patient. The occurrence of an adverse event will be based on changes in the patient's physical examination, laboratory results, and/or signs and symptoms.

All adverse events (except Grade 1 and 2 laboratory abnormalities that do not require an intervention), regardless of causal relationship, are to be recorded in the case report form and source documentation. The Investigator must determine the intensity of any adverse events according to the NCI Common Terminology Criteria for Adverse Events (CTCAE) Version 5.0 ([APPENDIX II](#)) and their causal relationship. Those AEs not covered by these criteria will be graded as follows:

1. Mild: Discomfort noticed, but no disruption of normal daily activity. Prescription drug not ordinarily needed for relief of symptom but may be given because of personality of patient.
2. Moderate: Discomfort sufficient to reduce or affect normal daily activity. Patient is able to continue in study; treatment for symptom may be needed.
3. Severe: Incapacitating, severe discomfort with inability to work or to perform normal daily activity. Severity may cause cessation of treatment with test drug; treatment for symptom may be given and/or patient hospitalized.
4. Life-Threatening: Symptom(s) place the patient at immediate risk of death from the reaction as it occurred; it does not include a reaction that, had it occurred in a more serious form, might have caused death.
5. Fatal: Event caused the death of the patient.

Adverse events will be followed until resolution or stabilization while the patient remains on-study. Once the patient is removed from study, events thought to be related to the study medication will be followed until resolution or stabilization, unless, in the Investigator's opinion the event is unlikely to resolve due to the patient's underlying disease, or until the patient starts a new treatment regimen or the patient is lost to follow-up.

8.1.2.2 Attribution Definitions

An adverse event is considered to be associated with the use of the Investigational Product if the attribution is determined as possible or definite. Attribution of AEs will be recorded in the CRF as:

- Unrelated: The AE is clearly NOT related to the study treatment.
- Possible: The AE may be related to the study treatment.
- Definite: The AE is clearly related to the study treatment.

8.1.2.3 Definition of an Unexpected Adverse Event

An unexpected adverse event is defined as any adverse drug experience, the specificity or severity of which is not consistent with the current Investigator Brochure; or, if an Investigator Brochure is not required or available, the specificity or severity of which is not consistent with the risk information described in this protocol or in the regulatory agency study authorization application.

Unexpected, as used in this definition, refers to an adverse drug experience that has not been previously observed (e.g., included in the Investigator Brochure) rather than from the perspective of such experience not being anticipated from the pharmacological properties of the pharmaceutical product.

8.1.2.4 Serious Adverse Event (SAE)

A serious adverse event is defined as any untoward medical occurrence that at any dose:

1. Results in death,
2. Is life-threatening (i.e., the patient was at risk of death at the time of the event. It does not refer to an event which hypothetically might have caused death if it was more severe),
3. Requires in-patient hospitalization or prolongation of existing hospitalization excluding that for pain management, disease staging/re-staging procedures, or catheter placement unless associated with other serious events,
4. Results in persistent or significant disability/incapacity, or
5. Is a congenital anomaly/birth defect.

Important medical events that may not result in death, be life-threatening, or require hospitalization may be considered serious adverse drug events when, based on appropriate medical judgment, they may jeopardize the patient or subject and may require medical or surgical intervention to prevent one of the outcomes listed above.

Disease Progression, or death as a result of disease progression, **are not considered to be SAEs**. However, if the progression of the underlying disease is greater than what would normally be expected as part of the natural course of the disease under study for the patient, or if the Investigator considers that there was a causal relationship between treatment with study drug or protocol design/procedures and the disease progression, then it must be reported as an SAE.

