2.6 Potential Risks and Benefits

As this is the first-in-man study of HS-130, no human data regarding the safety or potential benefit of HS-130 is available.

All currently available clinical data for HS-110 (viagenpumatumucel-L) suggest that this allogeneic cell therapy is safe and well tolerated in adults with NSCLC. Mild to moderate injection site reactions, especially induration, erythema, pruritus, pain and rash are expected as they indicate the vaccine has an immunogenic effect, but these have been well-tolerated. No significant safety concerns or risks associated with this allogeneic cell therapy have been reported.

To date, no clinically significant toxicities deemed by study Investigators as possibly, probably or definitely related to HS-110 (viagenpumatumucel-L) have been reported, nor have there been any HS-110 related deaths or SARs in the development program.

Please see the current Investigator Brochure for further details about the potential risks and benefits associated with this study.

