- i: Approximately 23 mL blood per draw Day 1 (pre-dose) and Day 8 for C1 and C2, and at 30-day safety follow-up visit for immune response labs (See Section 8.6).
- j: Cytokines and chemokines sample collection on Day 1 for C1 and C2 at time-points: Before HS130/HS110 treatment, and 2 hr ± 10 minutes after treatment. For C3 and beyond only if the patient is symptomatic i.e. flu-like symptoms, fever, or allergic reactions. (Approximately 3 mL blood per draw).
- k: Pre-treatment biopsy (archival tissue may be submitted if collected less than 6-months prior to C1D1 and the local pathologist confirms that an adequate amount of tissue/tumor cells exist to allow completion of all testing as outlined in the Specimen Collection Manual) and on-treatment biopsy collected within 5-14 days after patient completes 2nd dose of HS-130/HS-110 for genomic and proteomic analysis of exploratory biomarkers (e.g. mIHC). Biopsy should be collected for patients with accessible tumor lesions, incl. metastases (e.g. lymph node metastases) where it is considered feasible without a risk of complications for the patient. Coagulation parameters and blood cells should be assessed and reviewed per institutional standard prior to any biopsy.
- l: HS-130 and HS-110 will be administered via intradermal injections/re-injections (up to 10 total) on Day 1 of each cycle, depending on the assigned dose level. (See section 6.1 Drug preparation and administration)
- m: All assessments should be performed at 30 days ± 3 days after the last treatment, during the 30-day safety follow-up visit.
- n: If a patient stops treatment for any other reason than progressive disease, radiological assessments will continue every 12 weeks starting from the date of patient's last dose until disease progression or initiation of new anti-cancer treatment.
- o: Survival status and subsequent anti-cancer therapy information will be collected approximately every 12 weeks in a clinic visit, or by telephone from the time of disease progression or initiation of new anti-cancer treatment until death.
- p: Each cycle is 14 days.

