8.1.2.7 Reporting of Serious Adverse Events

Adverse events classified as serious require expeditious handling and reporting to Sponsor's monitoring CRO to comply with regulatory requirements. In general, reporting of Serious Adverse Events (SAEs) will begin at the time of first dosing on Cycle Day 1; however, SAEs occurring prior to first dosing may be reported if directly attributable to a study procedure.

For any serious adverse event (SAE) that occurs while a patient is on-study; within 30 days of the last study drug administration, regardless of any opinion as to the relationship of the SAE to the study drug; or if any SAE that the Investigator feels is related to the study drug occurs later than 30 days after the last study drug administration, the Sponsor or its designee must be notified immediately (within 24 hours of becoming aware of the event).

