9.2 Endpoints

9.2.1 Primary

- Safety and Tolerability: number of patients with TEAEs, SAEs, DLTs.

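### The SAE definition excludes hospitalization for pain management whatever its cause, so a pain-only admission caused by the injections or the on-treatment biopsy is not an SAE by default

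*Combined protocol and SAP*

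**What the plan says.** Section 8.1.2.4 lists five seriousness criteria. Item 3 covers an event that "Requires in-patient hospitalization or prolongation of existing hospitalization excluding that for pain management"; in full, the exclusion reads "excluding that for pain management, disease staging/re-staging procedures, or catheter placement unless associated with other serious events". It says nothing about the cause of the pain.

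A later paragraph of 8.1.2.4 adds a discretionary route: "Important medical events that may not result in death, be life-threatening, or require hospitalization may be considered serious adverse drug events" where medical judgment supports it. The closing paragraph removes disease progression from the SAE definition, but makes reporting mandatory again if the investigator sees a causal link to study drug or to the protocol's procedures.

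The primary endpoint in 9.2.1 is "Safety and Tolerability: number of patients with TEAEs, SAEs, DLTs". For an SAE, 8.1.2.7 requires that "the Sponsor or its designee must be notified immediately (within 24 hours of becoming aware of the event".

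Pain is foreseeable here. Section 2.6 says of HS-110 that "Mild to moderate injection site reactions, especially induration, erythema, pruritus, pain and rash are expected", and also that these reactions have been well tolerated. HS-130 has no human data. The footnotes to the Schedule of Assessments (7.1) require an "on-treatment biopsy collected within 5-14 days after patient completes 2nd dose of HS-130/HS-110", and inclusion criterion 2 does not accept fine-needle aspiration.

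**The concern.** An exclusion for pain admissions makes sense in an advanced-cancer trial when the pain comes from the tumour. Here the wording reaches further. It covers pain caused by the product or by a study procedure, which is what a first-in-human safety trial sets out to detect.

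Two things are at stake. One is the SAE count, a named component of the only primary endpoint, presented by dose cohort (section 9.0). The other is speed: an event not classed as serious does not trigger SAE notification within 24 hours. The number of injections also rises with dose level, so any local pain effect would be expected at the upper levels, where cohorts start with three patients.

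**Working it through.** The point turns on wording, and the plan has no figure of its own to reproduce. The check sets the sections side by side.

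1. **Is the pain exclusion limited anywhere?** The sections on adverse events (8.1.2.1), attribution (8.1.2.2), SAE definition (8.1.2.4), SAE reporting (8.1.2.7), DLTs (6.1.2) and safety analysis (9.3) contain no text restricting it to cancer pain, pre-existing pain or unrelated pain. The only qualifier is association with another serious event. I read that qualifier as applying to all three excluded admission types, which is the reading most favourable to the plan.

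2. **Contrast within 8.1.2.4.** The disease-progression exclusion has a causal exception covering both study drug and protocol procedures. The pain exclusion has none.

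3. **Does it reach the injections?** From Table 1 (6.1), injections per visit are:
   - level 1: 1 HS-130 + 1 HS-110 = 2
   - level 5: 2 + 4 = 6
   - level 6: 3 + 4 = 7
   - level 7: 3 + 7 = 10, taking seven HS-110 injections because 0.14 + 6 × 0.12 = 0.86 mL, the stated total; 10 is also the stated maximum

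   An admission only to control pain from these injections fails item 3.

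4. **Does it reach the biopsies?** The second dose is due on study day 15 (14-day cycles, ignoring the ±2-day window). The on-treatment biopsy therefore falls on day 15 + 5 = 20 to 15 + 14 = 29. Even if dose 2 is the last dose, 14 days is less than the 30-day SAE reporting period, so this biopsy lies inside it. The pre-treatment biopsy is different: under 8.1.2.7, "SAEs occurring prior to first dosing may be reported if directly attributable to a study procedure", so reporting there is optional whatever item 3 says, and archival tissue may replace that biopsy. The point rests on the injections and the on-treatment biopsy.

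5. **What else would catch the event?**

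| Route | Pain-only admission, related to injections | Pain-only admission, related to on-treatment biopsy |
|---|---|---|
| AE record and TEAE count (8.1.2.1, 9.2.1) | Yes | Yes |
| SRC review of non-serious AEs (8.1.2.8.1) | Yes | Yes |
| Immediate notice of a suspected DLT (6.1.2) | Possible, first 4 weeks only | Unlikely, as DLTs are treatment-related |
| DLT count (6.1.2) | Possible at Grade 3 or above, but not if Grade 3 and medically controllable | Unlikely |
| SAE by item 3 (8.1.2.4) | No | No |
| SAE as an important medical event (8.1.2.4) | Optional | Optional |

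6. **Do decisions change?** Escalation and the MTD use DLTs (6.1.1, 6.1.3). The stopping criteria use related deaths and Grade 4 events (5.5). Neither uses SAE status.

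7. **Size.** The expected number of misclassified patients would be the number treated times the rate of pain-only related admissions among patients with no other SAE. The documents give no such rate. One such patient would be 1/3 = 33 percentage points in a three-patient cohort, and 1/30 = 3.3 to 1/13 = 7.7 points over the planned 13 to 30 patients. That is what any single event does to a small denominator; it does not measure how large the problem is.

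**The case against.** The strongest reply is that the exclusion sits beside staging procedures and catheter placement, both routine cancer-care admissions, so the intent was probably to leave out disease-care pain. That is plausible, but the text does not say it. Sites classify events by the text, and the disease-progression paragraph shows that the plan states a causal exception when it wants one.

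The second reply is that the event stays visible. This stands: it is a TEAE, its CTCAE grade is recorded, the SRC sees it, and severe related pain in the first four weeks can reach the sponsor as a suspected DLT. It limits the consequence without correcting the classification. Treatment can continue well past week 4, when the DLT route has closed, and the TEAE count alone does not separate a patient admitted for pain from one with a mild reaction.

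The third reply is that such admissions may never occur. Section 2.6 expects mild to moderate reactions and reports no HS-110-related SARs, with over 100 patients treated (2.4). This also stands as a limit on likely frequency, although HS-130 and the combined re-injection have no human data.

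A reader might infer that related pain admissions can never be SAEs. The documents do not support that: an associated serious event, such as a serious infection or bleed after biopsy, lifts the exclusion, and medical judgment can bring a case back in.

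**Conclusion.** The gap is real and narrow. As written, a pain-only admission caused by the injections or the on-treatment biopsy is by default outside the SAE count and outside 24-hour SAE notification. Its size is unknown. The conclusion assumes that sites apply item 3 literally and do not use the optional important-medical-event route.

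Two stronger inferences are not supported. One is that the trial's tolerability result will be too favourable: that needs evidence that such admissions occur, and the documents offer none. The other is that dose escalation or stopping is compromised: no such rule depends on SAE status, and the analyses are descriptive, with no sample size calculation (9.6). A wording change is still worth making, because whether a treatment-related admission in a first-in-human trial counts as serious should not rest on discretion.

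**What to change.** In 8.1.2.4 item 3, replace the open pain exclusion with: *hospitalization for management of pain due to the underlying cancer and judged unrelated to study treatment or a study procedure*. The other two excluded admission types and the associated-serious-event qualifier can stay. This brings item 3 into line with the causal exception already written for disease progression. Pain admissions at least possibly related to HS-130, HS-110 or a study procedure during the SAE reporting period would then count as SAEs and be notified within 24 hours.

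The cost is a one-line amendment, possibly a few more SAE reports and a slightly less favourable SAE count. Because 8.1.2.2 defines attribution only against study treatment, the relation to a study procedure would need to be noted on the SAE report. Treatment, visits and analyses do not change.

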8.1.2.5 Reference Safety Information

The Reference Safety Information (RSI), in the current, approved Investigator's Brochure, is a list of expected Serious Adverse Reactions which are classified using Preferred Terms (PTs) according to the Medical Dictionary for Regulatory Activities (MedDRA). The RSI section will be used for assessing the expectedness of the study medication.

8.1.2.6 Pregnancy

Any pregnancy detected during the study, or that occurs within 30 days after stopping study medication, must be reported immediately to the Investigator. Pregnancy, in and of itself, is not regarded as an adverse event, unless there is suspicion that study medication may have interfered with the effectiveness of a contraceptive medication. If the patient becomes pregnant while on-study, the study drug should be immediately discontinued. Pregnancy information about a female patient or a female partner of a male patient should be reported immediately from the time the Investigator first becomes aware of a pregnancy or its outcome. This will be performed by the Investigator per instructions from the Sponsor, or its designee.

Any pregnancy complication, spontaneous abortion, elective termination of a pregnancy for medical reasons, outcome of stillbirth, congenital anomaly/birth defect, or serious adverse event in the mother will be recorded as an SAE and will be reported as described in Section [8.1.2.7](#).

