7. Patients, both females and males, of childbearing/reproductive potential must agree to use adequate contraception while included in the trial and for six months after the last treatment with HS-130 and/or HS-110.
8. Patients must be willing and have the capacity to sign the informed consent form.

Exclusion Criteria:

If any of the following apply, the patient **MUST NOT** enter the trial:

1. Have clinically significant cardiac disease, including:
 - Onset of unstable angina within 6 months of signing the Informed Consent Form (ICF).
 - Acute myocardial infarction within 6 months of the signing the ICF.
 - Known congestive heart failure (Grade III or IV as classified by the New York Heart Association); and/ or a known decreased cardiac ejection fraction (LVEF) of < 45%.
 - Uncontrolled hypertension defined as systolic blood pressure ≥ 160 mmHg and/or diastolic blood pressure ≥ 100 mmHg, despite optimal medical management.
2. Known or clinically suspected leptomeningeal disease. Stable, previously treated metastases in the brain or spinal cord, are allowed as long as these are considered stable (by CT or MRI), and not requiring systemic corticosteroids.
3. History of \geq grade 3 allergic reactions as well as known or suspected allergy or intolerance to any agent given in the course of this trial, live cell therapies, or live vaccines.
4. History of suspected cytokine release syndrome (CRS).
5. Known immunodeficiency disorders (testing not required).
6. Ongoing or current autoimmune disease. Permanent but stable and manageable immune related adverse events (irAE) from prior therapies are permissible, if prednisone equivalent corticosteroid use does not exceed 10 mg/day.
7. Any other condition requiring concurrent systemic immunosuppressive therapy (other than allowable exceptions which do not exceed 10mg/day of prednisone/corticosteroid use).
8. Major surgery (requiring general anesthesia or inpatient hospitalization) within four weeks before first IMP administration.

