5.0 SELECTION AND WITHDRAWAL OF SUBJECTS

5.1 Inclusion Criteria

Patients **must** meet all of the following inclusion criteria before they will be allowed to participate in the trial:

1. Patients with metastatic or advanced, unresectable solid tumor who have progressed, or recurred following standard-of-care (SOC) therapies or are ineligible for, or refuse, safe and effective SOC therapies and for whom, in the opinion of the Investigator, experimental therapy with HS-130/HS-110 may be beneficial.
2. Patients should have lesions that are safely accessible for biopsy and be willing to provide pre-treatment and on-treatment tissue biopsy. Fine-needle aspiration biopsy is not acceptable. Archival

tumor tissue will be accepted in lieu of fresh biopsy at screening if sample was collected within 6-months from Cycle 1 Day 1, and the local pathologist confirms that an adequate amount of tissue/tumor cells exist to allow completion of all testing as outlined in the specimen collection manual.

3. Age \geq 18 years.
4. Have an acceptable organ function:
 - Albumin \geq 2.5 g/dL.
 - Total Bilirubin $<$ 3.0 \times upper limit of normal (ULN) unless patient has Gilbert's syndrome.
 - Alanine transaminase (ALT) and aspartate transaminase (AST) \leq 3.0 \times ULN or \leq 5 \times ULN in the case of liver metastases.
 - Calculated or measured creatinine clearance $>$ 35 mL/minute per the Cockcroft-Gault formula.
 - Absolute neutrophil count \geq 1,500/mm³.
 - Hemoglobin \geq 9 g/dL.
 - Platelet count \geq 100,000/mm³.
5. Have an Eastern Cooperative Oncology Group (ECOG) performance status of 0 or 1.
6. Life expectancy of at least three months.
7. Patients, both females and males, of childbearing/reproductive potential must agree to use adequate contraception while included in the trial and for six months after the last treatment with HS-130 and/or HS-110.
8. Patients must be willing and have the capacity to sign the informed consent form.

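### Section 8.1.2.6 sets an explicit pregnancy reporting window of 30 days after treatment, while criterion 7 requires contraception for six months, and nothing scheduled later asks about pregnancy

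*Combined protocol and SAP*

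**What the plan says.** Inclusion criterion 7 (section 5.1, repeated in the synopsis) covers both sexes. Patients of reproductive potential "must agree to use adequate contraception while included in the trial and for six months after the last treatment with HS-130 and/or HS-110".

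Section 8.1.2.6 contains the reporting rule: a pregnancy found during the study, or one "that occurs within 30 days after stopping study medication", has to go to the Investigator at once. The section then makes three further statements that matter here:

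- On the Investigator's own duty, information about a pregnant patient, or the pregnant partner of a male patient, "should be reported immediately from the time the Investigator first becomes aware of a pregnancy or its outcome". No time limit is attached.
- "Pregnancy, in and of itself, is not regarded as an adverse event", except where the study medication is suspected of having interfered with a contraceptive.
- Complications, losses, stillbirths and birth defects are recorded as SAEs and follow section 8.1.2.7. More than 30 days after the last dose, that section requires notification only of SAEs the Investigator considers related.

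Table 3 and section 7.2 place the one pregnancy test before treatment. The 30-day safety visit (7.4), post-treatment follow-up (7.5) and survival follow-up (7.6) list neither a pregnancy test nor a pregnancy question.

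**The concern.** A sponsor normally asks for contraception after the last dose because it does not want a conception in that interval, and it normally collects pregnancies over the same interval so that any that occur are recorded. Here the precaution lasts six months and the only post-treatment reporting period given in figures lasts 30 days. The protocol does not say that the difference is intended.

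What is at stake is the completeness of safety data on a new product. Section 2.6 states that there are no human safety data for HS-130, and section 2.3.2 that no formal GLP toxicology studies of it have been done. In that setting even one pregnancy in the months after treatment, with its outcome, would be worth having on record. As the text stands, whether a pregnancy in month 3 is recorded may depend on how a site reads one phrase and on whether anyone happens to tell the Investigator.

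The primary endpoint, the DLT assessment and the escalation rules are not affected.

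**Working it through.** The plan gives no figure to reproduce, so the check compares the two periods and then looks for any other procedure that closes the gap.

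**Inputs.** Reporting window after stopping treatment: 30 days (8.1.2.6). Contraception after the last treatment: six months (criterion 7), taken as 180 to 184 days.

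**Step 1: the six months after treatment.** Share outside the explicit window = (six months − 30) / six months.

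- 180 days: (180 − 30)/180 = 150/180 = 83.3%
- 184 days: (184 − 30)/184 = 154/184 = 83.7%

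The window therefore covers 16.3% to 16.7% of the post-treatment period, and about five of the six months lie outside it.

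**Step 2: the whole contraception period.** Criterion 7 also covers time in the trial. Take that as T days on treatment, all of which the reporting rule covers, and six months as 182.6 days. Share outside = (182.6 − 30)/(T + 182.6). The documents give no expected treatment duration, so T is an assumption.

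| Assumed T | Calculation | Share outside |
|---|---|---|
| 28 days (4 weeks) | 152.6/210.6 | 72.5% |
| 112 days (16 weeks) | 152.6/294.6 | 51.8% |
| 168 days (24 weeks) | 152.6/350.6 | 43.5% |

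The share reaches one half when T = 2 × 152.6 − 182.6 = 122.6 days.

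**Step 3: does another procedure fill the gap?**

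- Section 7.4: the 30-day visit has no pregnancy test.
- Section 7.5: follow-up applies only to patients who stopped for a reason other than progression, and records medications, adverse events and imaging. Pregnancy is generally not an adverse event under 8.1.2.6, so collecting adverse events does not reliably pick it up.
- Section 7.6: survival follow-up collects survival status and later anti-cancer therapy.
- Section 8.1.2.7: a late SAE is notified if judged related. This depends on an outcome having already occurred and come to the Investigator's notice.
- Section 8.1.2.6: the Investigator's duty has no time limit, but it starts with awareness, and nothing scheduled creates awareness.

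None of these is routine collection of pregnancies between day 30 and month six.

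**The case against.** The strongest objection is that the reporting rule has two limbs, and the 30 days belong to the second only. The first turns on when a pregnancy is detected, the second on when it occurs. Section 4.2 ends the study at the last visit of the last patient, follow-up contacts run about every 12 weeks, and survival follow-up continues until death. If a patient in follow-up is still in the study, a pregnancy found in month 4 is already reportable. The 30-day limb would still do some work on this reading: it would catch a pregnancy that began within 30 days but came to light after the patient had left.

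This reading is possible, and it prevents the claim that reporting stops at 30 days. It is not clearly the intended one. The same section says "If the patient becomes pregnant while on-study, the study drug should be immediately discontinued", which ties being on study to receiving drug, and Table 3 shows its entries spanning the study separately from the follow-up columns. The text is ambiguous, and the ambiguity itself needs correcting.

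A reader might also infer that pregnancies in months 2 to 6 would be lost to the safety record. The documents do not support that, because a pregnancy known to the Investigator must be passed on whenever it becomes known, and related late SAEs remain reportable. Nor does the protocol describe those months as a period of exposure; that is an inference from the contraception requirement, which may be purely precautionary. Sponsor instructions on pregnancy reporting, which 8.1.2.6 mentions, may add detail that is not visible here.

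Finally, few pregnancies are likely among 13 to 30 patients with advanced solid tumors. That is fair, and it limits the importance of the point.

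**Conclusion.** The mismatch is real and minor. The only post-treatment reporting window stated in figures is 30 days, against six months of required contraception, and no later contact is designed to find a pregnancy. On the narrower reading of the study period in 8.1.2.6, about 150 of roughly 180 post-treatment days (83%) have no explicit requirement to report a pregnancy to the Investigator.

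The 83% rests on that reading and applies only to the six months after treatment. It should not be quoted for the whole contraception period, where the share depends on treatment duration and falls below half once treatment exceeds about 123 days. On the broader reading, the explicit duty extends into follow-up, and what remains is the absence of any scheduled question and an undefined term.

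This is a low-cost improvement to safety data collection.

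**What to change.** Reconcile section 8.1.2.6 with criterion 7 in section 5.1 and the synopsis:

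- Replace the 30-day phrase in 8.1.2.6 so that pregnancies in patients and in female partners of male patients are reportable to the end of the contraception period stated in criterion 7. Tying the window to that criterion keeps the two together if either is amended, and removes the dependence on what counts as the study period. Outcomes are handled as 8.1.2.6 already describes.
- Add a pregnancy question to the follow-up contacts in sections 7.5 and 7.6. Counted from the last dose, as in 7.5, 12-weekly contacts fall at about days 84 and 168. The question should therefore also be asked at the first contact after the six months end, to pick up a late conception.

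The cost is one phrase, one question at contacts already scheduled, and a somewhat longer reporting and outcome follow-up duty for sites. No visit or test is added, and the dosing and contraception rules stay as they are.
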